### ***Subject Selection***

The study will be performed after the approval of the Ethics Committee of the Universitat Internacional de Catalunya (UIC) and will be conducted according to the principles outlined in the Declaration of Helsinki and Ethical Conduct for Research with Human Beings.

An aleatoric list of patients who have been enrolled in SPT at the Department of Periodontology of UIC and met the inclusion criteria will be generated – those patients will be called for SPT visit by the same investigator ([name])

Criteria for subject selection will be as follows:

- (1) Patients aged 18 to 80 years who are healthy;
- (2) Partially edentulous patients, rehabilitated with at least one dental implant in the maxilla or mandible;
- (3) No implant mobility;
- (4) Treated periodontal disease;
- (5) No systemic diseases that could influence the outcome of the therapy (i.e. uncontrolled diabetes, osteoporosis, bisphosphonate medication).
- (6) Non-smoker or light smoking status in smokers (<10 cigarettes/day).

Pregnant, lactating women and non-collaborating patients will be excluded from the study.

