Nevertheless, even though SPT is considered to be crucial to maintain peri-implant health, classic studies have shown that patient's adherence to SPT is not satisfactory (Wilson et al., 1984). Several studies have been carried out in different settings involving a considerable variety of cohorts of patients coming from both university and private practices in order to assess the factors that are associated with the lack of compliance with SPT (Ramseier et al., 2014, Perrell-Jones and Ireland, 2016). Identifying patients who are more likely to present a non-compliant pattern would help clinicians to focus their attention on these particular subjects, who mostly require a motivational strategy tailored to each individual risk profile (Amerio et al., 2019). The same publication pointed out that smoking habit and history of periodontal disease were found to be associated with patients' compliance. Inadequate information/motivation was found as the main patient-reported reason for non-compliance.

Addressing the main reason for patients' non-compliance is a research priority; however, studies in the literature are scarce. It's crucial that clinicians understand the importance of supportive periodontal treatment to prevent the development and progression of peri-implant diseases (Schwarz et al., 2018). Therefore,

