#### b) Specific Hypothesis

1. SPT with conventional ultrasonic device will result in more pain/discomfort around dental implants than in teeth.
2. SPT by means of an erythritol based air-polishing powder (Air Flow Master®, Air-Flow Plus®, EMS, Nyon, Switzerland) will result in better patient reported outcomes and same clinical outcomes, at the first SPT and after 2 years.
3. SPT by means of an erythritol based air-polishing powder (Air Flow Master®, Air-Flow Plus®, EMS, Nyon, Switzerland) will result in the increase of the compliance rates after 2 year of follow-up.

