## **SPECIFIC COMMISSION OF THE DOCTORAND**

years of follow-up. Additionally, a periapical radiograph of all implants involved in the study will be taken at 1 year and 2 years of follow-up. Individual compliance will be registered as well in the CRF.

Patients will be further motivated with respect to oral hygiene habits during the entire period of the study.

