### **Anthropometric and socio-demographic data**

An initial questionnaire will be conducted to obtain information regarding age, race, gender, medical history, medication, and health behavior (smoking habits). Smoking behavior will be specified as 3 categories: never smoker, former smoker, or current smoker (light smokers: < 10 cigarettes/day). Patients will be asked about their tobacco smoke exposure in terms of consumption (i.e. the number of cigarettes consumed per day); duration (i.e. the number of years of smoking); and lifetime exposure (i.e. the accumulated exposure as formed by the product of consumption and duration: cigarette-years). In case of former smokers, patients will be asked about the smoke-free time following cessation.

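### Hypothesis 3 predicts a rise in SPT compliance, but prior attendance is not listed at baseline: no within-patient rise can be shown, chance imbalance stays hidden, and a ceiling is possible

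*Combined protocol and SAP*

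**What the plan says.** Specific Hypothesis 3 expects that SPT with the erythritol powder "will result in the increase of the compliance rates after 2 year of follow-up". It does not say whether the increase is measured against the control arm or against the patients' own past. Specific objective 3 asks for the effect on compliance at 1 and 2 years. Compliance is listed under Secondary outcome; the main outcome is VAS pain.

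Subject Selection starts from "An aleatoric list of patients who have been enrolled in SPT at the Department of Periodontology of UIC", and "those patients will be called for SPT visit by the same investigator". It closes with "Pregnant, lactating women and non-collaborating patients will be excluded from the study". Under Randomization and study groups, allocation is revealed at that visit, after oral hygiene instruction.

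The baseline data are described in two main places. Screening examination covers history forms, anthropometric, socio-demographic and clinical information, probing, plaque and radiographs. Anthropometric and socio-demographic data says: "An initial questionnaire will be conducted to obtain information regarding age, race, gender, medical history, medication, and health behavior (smoking habits" (the quoted parenthesis closes there), followed by detail on tobacco exposure. Neither section lists earlier SPT attendance. Compliance enters the CRF under Follow-up visits, and Compliance Definition classes patients as regular (RC), erratic (EC) or non-compliers (NC). No expected or historical compliance rate is given.

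**The concern.** An increase needs a reference value. If it means more regular attendance than the same patients showed before, the plan lists nothing to measure it from. If it means more than control, randomisation supplies the reference, but two weaknesses remain.

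First, past attendance is a plausible strong predictor of later attendance. With about 15 patients per arm it may differ by chance, and as planned nobody could see that or adjust for it.

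Second, entry is through a visit that the patient attends, from a list of patients already in SPT. That tilts the sample towards attenders. If most control patients remain regular compliers, the test arm has little room to do better, and a null result could be misread as showing that the device does not affect compliance. Improved adherence is also the project's General Hypothesis, so this reading matters even though the outcome is secondary.

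**Working it through.** **1. The plan's own sample size.** Inputs from Sample Size Calculation: difference 1 mm in CAL, SD 0.9, alpha 0.05 (taken as two-sided), power 80%, loss 12%.

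n per arm = 2 × [0.9 × (1.960 + 0.842)]² / 1² = 12.7, so 13. Allowing for loss: 13 / 0.88 = 14.8, so 15 per arm and 30 in total. The stated figure reproduces, but it was set for CAL and not for compliance. Below, 15 is the number randomised and 13 the number left after loss.

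**2. How much room a ceiling leaves.** Assumptions made here, not in the plan: compliance is split into RC versus not RC and compared by a two-sided Fisher's exact test. The Inferential analysis section assigns no test to compliance. Take the best case, in which every test patient is RC. With k control patients not RC and n per arm, p = 2 × C(n,k) / C(2n,k).

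- 15 per arm, control 11/15 (k = 4): 2 × 1365 / 27405 = 0.0996.
- 15 per arm, control 10/15 (k = 5): 2 × 3003 / 142506 = 0.042.
- 13 per arm, control 9/13 (k = 4): 2 × 715 / 14950 = 0.096.
- 13 per arm, control 8/13 (k = 5): 2 × 1287 / 65780 = 0.039.

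So even a perfect test arm reaches significance only if control has at most 10/15 (67%) or 8/13 (62%) regular compliers.

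**3. Best-case power.** This is the binomial probability that control has at most 10 of 15, or at most 8 of 13, regular compliers. The control rates are assumed.

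| Control RC rate | 15 per arm | 13 per arm |
|---|---|---|
| 50% | 94% | 87% |
| 60% | 78% | 65% |
| 70% | 48% | 35% |
| 80% | 16% | 10% |
| 90% | 1% | 0.6% |

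Best-case power reaches 80% only at a control rate of about 59% or lower (15 per arm) or about 54% or lower (13 per arm).

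**4. How much of this is sample size.** For a 20-point rise starting from 50%, 60% or 70%, exact Fisher power at 15 per arm is 10%, 11% and 15%. The number needed for 80% power, with p̄ the mean of the two rates, is

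n = [1.960 × √(2p̄(1−p̄)) + 0.842 × √(p₁(1−p₁) + p₂(1−p₂))]² / (p₂ − p₁)²

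For 50% to 70%: (1.358 + 0.571)² / 0.04 = 93 per arm. The same formula gives 82 (60% to 80%), 62 (70% to 90%) and 35 (80% to 100%), all before loss. The trial is therefore short of patients for Hypothesis 3 with or without a ceiling.

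**5. Chance imbalance in prior attendance.** Suppose 15 of the 30 patients had been regular attenders (assumed). With 15 per arm, the probability of a split no more uneven than 7 to 8 is 2 × C(15,7) × C(15,8) / C(30,15) = 2 × 6435² / 155117520 = 53%. The arms therefore differ by at least 3 patients (20 percentage points) in the other 47% of allocations. With 21 of 30 regular, the probability of a 10 to 11 split is 2 × C(15,10) × C(15,11) / C(30,21) = 2 × 3003 × 1365 / 14307150 = 57%, which leaves 43%.

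**The case against.** The strongest reply is that the trial is randomised with a concurrent control. A reader might infer from the missing baseline that no increase can be shown at all. The documents do not support that: objective 3 reads naturally as a test-versus-control effect, and that comparison needs no attendance history. What is lost is the before-after reading and the covariate. This objection stands.

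A reader might also infer that a ceiling is established. It is not. The background sections describe adherence to SPT as unsatisfactory, enrolment in SPT is not the same as regular attendance, and at a 50% control rate the best case is well powered. Entry by attending is inferred from the order of events and is hard to avoid, since the device is used at a visit. The Fisher threshold would apply to any trial of this size, however its patients were chosen.

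Three supporting arguments are tempting but weak.

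- "Pregnant, lactating women and non-collaborating patients will be excluded from the study" could be read as removing poor attenders. The term is undefined and may mean patients who cannot cooperate with procedures.
- Heavier smokers are excluded, and the background reports that "smoking habit and history of periodontal disease were found to be associated with patients' compliance". It gives no direction for either factor, and treated periodontal disease is itself an entry criterion.
- "Patients will be further motivated with respect to oral hygiene habits during the entire period of the study" concerns hygiene habits rather than attendance, and it applies to both arms.

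None of these carries the point. It is also fair that the screening visit collects clinical information in general terms, so prior attendance is best described as not listed, rather than as certain not to be recorded.

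**Conclusion.** The point holds in a limited form. The between-arm comparison of compliance is valid. As planned, however, Hypothesis 3 cannot support a statement that patients' compliance rose from its earlier level, and an imbalance in prior attendance, which is quite likely by chance at this size, would go unseen and unadjusted. A ceiling is a possibility whose size depends on a control rate that the documents do not give: best-case power at 15 per arm runs from 94% at 50% to 1% at 90%. These figures assume an RC versus not-RC split, Fisher's exact test and a perfect test arm, and they mainly reflect the small sample, which is a separate and larger limit that this point does not resolve. The main VAS outcome is unaffected. The change is worth making because it is cheap and does not depend on whether a ceiling occurs.

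**What to change.** - Under Screening examination, add that before allocation each patient's SPT attendance over the previous 24 months is taken from department records, or over the time in SPT if shorter. Treat lockdown absences as Compliance Definition already does. That the records are available is an assumption to confirm.
- State that Hypothesis 3 is a test-versus-control comparison in patients currently attending SPT.
- In Inferential analysis, analyse compliance at 1 and 2 years with prior attendance as one covariate, either visits per year or RC versus not RC. Do not stratify by three prior classes: with 13 to 15 patients per arm, cells would be sparse or empty.
- Report prior attendance by arm, and give the control-arm RC rate beside any null result so that a ceiling would be visible.

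The cost is a record look-up for about 30 patients and a narrower compliance claim. Eligibility and sample size do not change, and the low power for compliance remains.

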### ***Sample Size Calculation***

The sample size will be calculated using changes in CAL as the primary outcome variable. Thirty patients (15 subjects in each group) were necessary to detect a difference of  $\geq 1$  mm in CAL assuming a mean standard deviation (SD) of 0.9. This calculation assumes an alpha error of 0.05, a beta error of 0.2, and a statistical power of 80%. In addition, 12% of loss to follow-up was considered.

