### **Screening examination**

The clinician will review with the patient the Information and Medication History Forms and record the anthropometric, socio-demographic and clinical information. Candidates will undergo an oral pathology examination and a full-mouth manual probing using a periodontal probe PCP-UNC 15 (HuFriedy®, [name]) to determine their periodontal and peri-implant status. Presence or absence of plaque will be recorded after staining with an erythrosine disclosing dye (Plac-Control®, Dentaid SL, Cerdanyola, Spain). Finally, periapical radiographs (Dürr Dental AG, Bietigheim-Bissingen, Germany) of all implants will be taken using a paralleling cone technique and a film-holder (7mA- 60kV/20ms).

The same calibrated examiner ([name]) will record clinical variables of mPI, BOP, PPD, MR and clinical attachment level (CAL).

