### **VAS**

After finishing the supragingival debridement around teeth, another calibrated examiner ([name]) will give the patients graded pain intensity on a visual analogue scale (VAS) (0 = no pain and 10 = extreme, unbearable pain), and then perform supragingival debridement around the dental implants and give VAS again. Patients will be instructed to point at the VAS.

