## SPECIFIC COMMISSION OF THE DOCTORAND

Score 0 - no detection of plaque.

Score 1 - plaque only recognized by running a probe across the smooth marginal surface of the implant.

Score 2 - plaque can be seen by the naked eye.

Score 3 - abundance of soft matter.

6. mBI (Mombelli et al., 1987) will be assessed 30 seconds after 0.15 N force probing.

Score 0 - no bleeding.

Score 1 - isolated bleeding spots visible.

Score 2 - blood forms a confluent red line on margin.

Score 3 - heavy or profuse bleeding. This variable will be dichotomized in presence/absence of bleeding and will serve as the main variable.

7. SOP evaluated after assessing dichotomously the presence of suppuration within 30 seconds after gentle probing.
8. Implant PPD, measured from the mucosal margin to the bottom of the probable pocket, determined at six aspects per implant: mb, b, db, ml, l and dl with a resin splint.
9. MR at the implant will be recorded at six aspects per implant: mb, b, db, ml, l and dl.

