### ***Outcomes of the study***

#### **Main outcome;**

- Patient Pain/Discomfort (VAS) reported after decontamination during SPT.

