#### **Secondary outcome;**

- *Changes in the following clinical variables: FMPI, FMBI, PPD, GR, mPI, mBI, SOP, Implants PPD and MR after decontamination during SPT.*
- Compliance to SPT reported after decontamination during SPT.

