#### *Inferential analysis*

Data will be calculated at patient level and implant/tooth level. VAS score will be considered as the main outcome (quantitative).

If the distribution is normal, the following tests will be used:

- Binary categorical variables: T-Student / Fisher's exact test;
- Categorical variables with > 2 categories: ANOVA;
- Quantitative variables: Simple linear regression / Pearson correlation coefficient.

If it doesn't follow normality:

- Binary categorical variables: U of Mann-Whitney;
- Categorical variables > 2 categories: H of Kruskal-Wallis;
- Quantitative variables: Spearman's correlation coefficient.

[figure not shown]

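### The sample size and its 80% power are for CAL change, but the declared main outcome is VAS pain, for which no power is given

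*Combined protocol and SAP*

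**What the plan says.** All of these statements are in the combined protocol and SAP, under Materials and Methods unless noted.

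- **Sample Size Calculation:** "The sample size will be calculated using changes in CAL as the primary outcome variable". The inputs are a difference of at least 1 mm, SD 0.9, alpha 0.05, 80% power and 12% loss to follow-up. The result is 30 patients, 15 per group.
- **Main outcome:** "Patient Pain/Discomfort (VAS) reported after decontamination during SPT".
- **Inferential analysis:** "VAS score will be considered as the main outcome (quantitative)".
- **Clinical Parameters, item 6 (mBI):** "This variable will be dichotomized in presence/absence of bleeding and will serve as the main variable".
- **Secondary outcome:** "Changes in the following clinical variables: FMPI, FMBI, PPD, GR, mPI, mBI, SOP, Implants PPD and MR after decontamination during SPT", plus compliance. mBI is in this list; CAL is not.
- **Screening examination:** the examiner "will record clinical variables of mPI, BOP, PPD, MR and clinical attachment level (CAL)". CAL is therefore measured, although it is not among the nine numbered clinical parameters.
- **VAS:** patients score pain after debridement of the teeth; the examiner will "and then perform supragingival debridement around the dental implants and give VAS again". Each visit so described yields two scores.
- **Specific Hypothesis (section 4):** hypothesis 1 is that "SPT with conventional ultrasonic device will result in more pain/discomfort around dental implants than in teeth". Hypothesis 2 concerns patient-reported outcomes with erythritol air-polishing, both at the first SPT visit and at 2 years.

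**The concern.** A sample size should be justified on the variable that decides the trial. Here the only power statement belongs to CAL change, which is labelled primary in one section and is then missing from both outcome lists. The variable that two other sections call the main outcome has no target difference, no SD and no power. A reader cannot tell what VAS difference the trial could detect, and a null VAS result could not be interpreted against any planned difference.

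There is a second consequence. VAS is scored at two sites, is of interest at two time points, and serves two different comparisons: between arms, and teeth versus implants within patients. Since none of these is singled out, the VAS result reported as primary could be chosen after the data are seen.

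**Working it through.** **1. Reproduce the plan's figure (CAL).** Inputs are from the Sample Size Calculation section; a two-sided test is assumed, because sidedness is not stated.

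n per arm = 2(z₀.₉₇₅ + z₀.₈₀)²(SD/difference)² = 2(1.96 + 0.8416)²(0.9/1)² = 12.7, rounded up to 13.

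Allowing for 12% loss: 13/0.88 = 14.8, rounded up to 15 per arm, 30 in total. This matches the plan. By the noncentral t the answer is 14 per arm, or 16 after loss (32 in total). A one-sided normal calculation gives 11 per arm and 25 or 26 in total, which does not match. The CAL arithmetic is not at fault.

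**2. Can it be carried over to VAS?** No. The 1 mm and the 0.9 are millimetres of attachment; VAS is a 0 to 10 pain score. The documents give neither a VAS SD nor a VAS difference.

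**3. What 15 per arm can detect on VAS.** First-visit VAS is scored at the randomisation visit, so I apply no follow-up loss. For a two-sample t test, two-sided alpha 0.05, power comes from the noncentral t with 2n − 2 degrees of freedom and noncentrality d√(n/2), where d = difference/SD. Solving for 80% power:

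- n = 15 per arm: d = 1.06
- n = 13 per arm (2-year VAS after 12% loss): d = 1.15

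The table converts this to points. **Every SD in it is my assumption.**

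| Assumed VAS SD | Detectable at 80%, 15 per arm | Power for 1 point | Power for 1.5 points | Power for 2 points | n per arm for 80%: 1 point / 2 points |
|---|---|---|---|---|---|
| 1 | 1.06 | 75% | 98% | >99% | 17 / 6 |
| 1.5 | 1.59 | 42% | 75% | 94% | 37 / 10 |
| 2 | 2.12 | 26% | 51% | 75% | 64 / 17 |
| 2.5 | 2.65 | 18.5% | 36% | 56% | 100 / 26 |
| 3 | 3.18 | 14% | 26% | 42% | 143 / 37 |

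Fifteen per arm gives 80% power for 2 points only if the SD is no more than 2/1.06 = 1.89. With 13 per arm at 2 years, the detectable difference is 1.15 to 3.44 points over the same SDs.

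**4. The within-patient contrast.** For teeth versus implants in the 15 control patients (hypothesis 1), a paired t test has 80% power at 0.78 SD of the paired difference. That SD is a different quantity from the between-patient SD in step 3, so the two figures cannot be ranked against each other. One power sentence cannot cover both contrasts.

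**5. Effect of the test used.** The plan moves to Mann-Whitney if normality fails. Simulating normal data with 15 per arm, Mann-Whitney has about 76% to 78% power at 1.06 SD and needs about 1.1 SD for 80%.

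**The case against.** The strongest reply is that much of this is labelling.

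- **mBI.** The phrase sits inside the clinical parameters list and may mean the main variable among those. That is a fair reading, though the text does not say so. I treat mBI as a wording point; the CAL/VAS conflict does not depend on it.
- **CAL.** Its components, probing depth and recession, are listed as secondary outcomes, so the measurements exist. True, but CAL change itself, the powered variable, is not listed, and its components are not primary.
- **Adequacy for VAS.** Fifteen per arm might be enough. With an SD of 1, power for 2 points exceeds 99%. This stands, and it is why I do not say the trial is underpowered. Without an SD or a target difference, nobody can check either way.
- **Timing.** A figure in the statistical analysis section and a timeline diagram are not reproduced in the text I have, and might show when VAS is taken. They could settle the schedule, but the stated outcome and analysis text still chooses no primary site, visit or comparison.
- **Population for hypothesis 1.** The related objective is not limited to ultrasonic treatment. With all 30 patients the paired figure would be 0.53 SD rather than 0.78. This shows again that the contrast is not pinned down.

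**Conclusion.** The concern holds and must be fixed. The plan names CAL change as primary for the sample size and VAS as the main outcome elsewhere, and its 80% power applies only to the former. The contradiction and the absence of any VAS power statement rest on the text alone.

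The size of the gap for VAS cannot be settled from the documents. What can be said without an SD is that 15 per arm gives 80% power for a between-arm difference of 1.06 SD (two-sided t test, roughly normal data), or 1.15 SD with 13 per arm. The conversion to points, and every power figure in points, depends on the assumed SD of 1 to 3.

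**What to change.** Issue a dated amendment that does the following.

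1. Keep VAS as the only primary outcome, and fix one site, one visit and one comparison. VAS at implants, first SPT visit, test versus control fits the trial's rationale, but the sponsor should confirm the choice.
2. Remove the primary label from CAL in the sample size section and list CAL change as secondary. Delete the main-variable phrase for mBI, or qualify it as the main clinical parameter.
3. Label the other VAS measurements, and the within-patient teeth-versus-implant contrast, as secondary.
4. Restate the sample size paragraph for VAS with N unchanged: 15 per arm gives 80% power for 1.06 SD by a two-sided 5% t test (about 1.1 SD if Mann-Whitney is used). Give the assumed SD, its source and the resulting difference in points.
5. State beside it the smallest VAS difference the sponsor wants to detect. If that is below the detectable difference, record it as a limitation.

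The COVID-19 lockdown text under Compliance Definition suggests follow-up may already have begun; the documents do not say. The amendment should therefore record that VAS data by arm had not been seen. If they had, it should say that the choice is post hoc.

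The cost is one amendment and no extra patients. The downside is that the stated detectable VAS difference may look less favourable than the present text implies.

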### ***Withdrawal of consent***

The Patient Information Sheet will clearly state that the patient can withdraw from the study at any time without prejudice or explanation. Such withdrawal will be documented in the medical record file. Losses to follow-up are taken into account in the sample size calculations (12%).

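### The 30 patients already include the 12% loss, but the stated 80% power comes from a normal approximation; by the listed t-test it is about 78% for CAL (minor)

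*Combined protocol and SAP*

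**What the plan says.** The Sample Size Calculation section names its variable: "The sample size will be calculated using changes in CAL as the primary outcome variable". It then states: "Thirty patients (15 subjects in each group) were necessary to detect a difference of" 1 mm or more, "assuming a mean standard deviation (SD) of 0.9". On error rates it says "This calculation assumes an alpha error of 0.05", with "a beta error of 0.2, and a statistical power of 80" per cent. It closes with "In addition, 12% of loss to follow-up was considered". It gives neither the formula nor the sidedness of the test, and it does not say whether 30 is the number enrolled or the number evaluable.

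The Withdrawal of consent section returns to the loss: "Losses to follow-up are taken into account in the sample size calculations (12" per cent).

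The Inferential analysis section lists tests by type of variable. Under normality, the entry for a two-group comparison is "Binary categorical variables: T-Student / Fisher's exact test". If normality fails, the entry is Mann-Whitney. The section is a general list, and the only outcome it names is the VAS score.

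**The concern.** Once 12% of 30 patients are lost, about 26 remain, or 13 per arm. The question is whether those 13 per arm deliver the stated 80% under the test the plan lists. With so few degrees of freedom, a t-test needs somewhat more patients than the normal formula suggests, so a size taken from that formula can fall short.

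The opening words of the loss sentence add a second uncertainty. They can be read as a loss on top of the 30, which would make 30 the evaluable number.

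The stakes are modest. The plan commits to CONSORT reporting, so the sample-size statement is likely to be repeated in the trial report. It should then be true of the design and test described.

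**Working it through.** **Inputs.** From the Sample Size Calculation section: difference 1 mm, SD 0.9, alpha 0.05, power 80%, loss 12%, 15 per arm. From Inferential analysis: Student's t-test. Assumption: two-sided alpha, since sidedness is not stated. The standardised difference is d = 1/0.9 = 1.111.

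**Step 1: reproduce the plan's figure.** The normal-approximation formula is n per arm = 2 × (z₀.₉₇₅ + z₀.₈₀)² × SD² / difference².

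- 2 × (1.960 + 0.842)² × 0.81 / 1 = 12.7, rounded up to 13 evaluable per arm.
- 13 / 0.88 = 14.8, rounded up to 15 enrolled per arm, 30 in total.

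This matches exactly. A one-sided normal calculation gives 11 per arm, and 11/0.88 = 12.5, or 13 enrolled, which does not match. So the two-sided formula with the loss included is the version that yields the plan's number.

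**Step 2: evaluable patients.** 30 × 0.88 = 26.4, or 13.2 per arm.

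**Step 3: power by the normal formula.** At 13 per arm, d × √(n/2) = 1.111 × √6.5 = 2.833. Power = Φ(2.833 − 1.960) = Φ(0.873) = 80.9%. The 80% is therefore correct under the formula that produced the 30.

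**Step 4: power by the t-test.** The non-centrality parameter is the same 2.833, on 24 degrees of freedom, with critical value 2.064 in place of 1.960. From the noncentral t distribution, two-sided 5%:

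| Evaluable per arm | t-test power |
|---|---|
| 13 | 77.6% |
| 13.2 (expected number, unrounded) | 78.3% |
| 13 and 14 | 79.2% |
| Averaged over random 12% loss from 15 per arm | 77.9% |
| 14 | 80.8% |
| 15 (no loss) | 83.6% |

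**Step 5: size needed for 80% by the t-test.** The solution is 13.75, rounded up to 14 evaluable per arm. 14/0.88 = 15.9, or 16 enrolled per arm and 32 in total, which is two more patients than planned.

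**Step 6: the other reading of the loss sentence.** If 30 were the evaluable number, t-test power would be 83.6% and enrolment would have to be about 30/0.88 = 34.1. No such enrolment appears in the document. The exact match in Step 1 and the Withdrawal of consent section both point to 30 as the enrolled number.

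**The case against.** The strongest reply is that nothing has been miscalculated. The 30 follows exactly from a standard formula, and under that formula 13 per arm has 80.9% power. The gap against the t-test is 2.4 points at 13 per arm, 1.7 points at 13.2 and 0.8 points with 13 and 14 completers. The SD and the loss rate are themselves assumptions, and error in them could matter more. The t-test is also an inference for CAL, because the list of tests is generic and names only VAS. All of this stands. It makes the point minor but does not make 80% the power of the listed two-sided t-test.

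Four stronger readings are tempting, and the documents do not support them.

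- **That the plan ignored dropout.** It did not. The 30 reproduces only with the loss included, and the Withdrawal of consent section says so.
- **That 30 enrolled, 12% loss and 80% power cannot hold together on any reading.** They do hold under the normal formula. With a one-sided 5% t-test, which the text does not exclude, power at 13 per arm would be 86.6%.
- **That power falls to about 74% under the Mann-Whitney fallback.** That value arises only when the test is applied to simulated normal data, whereas the plan uses it when data are not normal. For non-normal data, power can be higher or lower depending on the shape of the distribution.
- **That losses will exceed 12% because the introduction calls SPT adherence unsatisfactory.** That remark concerns recall attendance in earlier studies. In this trial, erratic and non-compliance are outcome categories, which is not the same as loss to follow-up.

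**Conclusion.** The point holds in a limited form. The sample size is reproducible and already contains the 12% loss. The stated 80% is a normal-approximation figure. Under the listed Student t-test, the design has about 78% power for a 1 mm difference in CAL change, a shortfall of about 2 points or two enrolled patients. This rests on two-sided 5% testing, SD 0.9, 12% loss and the t-test being the one applied to CAL.

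A reader might take either 80% or 78% as the trial's power for its main question. The documents do not support that. The main outcome is VAS pain/discomfort, CAL is absent from the listed secondary outcomes, and no VAS difference or SD is given from which power could be computed. That mismatch is the larger problem in the same section, and this correction does not resolve it. Minor priority.

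**What to change.** Replace the sample-size statement with wording such as:

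> Thirty patients will be enrolled (15 per arm). Allowing for 12% loss, about 13 per arm will be evaluable, giving about 78% power (t-test, two-sided 5%) for a 1 mm difference in CAL change with SD 0.9.

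Remove the opening words of the loss sentence that suggest the 12% comes on top of the 30. If one-sided testing was intended, say so and recompute. Add that the figure applies to CAL and not to VAS.

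This is a change of wording only, and its one cost is a slightly less favourable stated power. If the sponsor prefers to keep 80%, the consistent t-test figures are 14 evaluable and 16 enrolled per arm (32 in total), which also fills eight complete blocks of four. If the trial is re-sized on VAS, that calculation replaces this one, and it should likewise state the test, the sidedness and whether the number is enrolled or evaluable.
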